8.5 Safety Analyses

All outputs for safety outcomes will based on FAS and SAF.

8.5.1 Adverse Events

An AE is defined as any undesirable clinical occurrence in a patient. An AE does not necessarily have a causal relationship with the study medical device. AEs will be recorded since date of informed consent signature until 30 days after any ablation procedure except SAEs with 36 months follow-up period.

Adverse events will be summarized by System Organ Class (SOC) and Preferred Term (PT) and broken down further by maximum severity and relationship to study device or procedure. Number (n) and percentage (%) will be presented with the percentage calculated relative to the total number of subjects in the FAS/SAF as following:

- AE Overview (subgroup by initial only and repeat ablation, run-in analysis set and full analysis set, and total count of safety analysis set)
- AE by SOC and PT
- Procedure related AE by SOC and PT
- Study device related AE by SOC and PT
- Serious AE by SOC and PT
- Procedure related serious AE by SOC and PT
- Study device related serious AE by SOC and PT
- AE by SOC, PT, and maximum severity
- AE by SIR and PT
- AE listings will be prepared. Information including SIR, PT, relationship with device/procedure, seriousness, severity, AE start and end date, intervention/treatment taken, outcome of AEwill be presented.

AEs will be coded using MedDRA Version 19.0 or higher.

Procedure-related AE

A procedure-related AE is an adverse event related to the study procedure. The relationship with study procedure is recorded as "Unlikely related", "Possibly related", "Probably related", and "Causal relationship".

Device-related AE

A device-related AE is an adverse event related to the use of the study device. The relationship with study device is recorded as "Unlikely related", "Possibly related", "Probably related" and "Causal relationship". Events marked with missing relationship with study device is considered as device-related AE.

Serious Adverse Event (SAE)

A Serious Adverse Event is any AE that:

- Resulted in death: An AE that resulted in the patient's death.
- Life-threatening illness or injury: The patient was at imminent risk of dying at the time of the AE.
- Permanent Impairment: An AE that resulted in permanent impairment of a body function or permanent damage to a body structure.
- Required in-patient or prolonged hospitalization. Note: If a patient has prolonged hospitalization due to having an additional ablative procedure to enhance the ablative margin and for no other adverse event, this should not be considered an SAE.
- Resulted in medical or surgical intervention to prevent life threatening illness or injury or permanent impairment to a body or body function
- Led to fetal distress, fetal death or congenital abnormality or birth defects.
- A persistent or significant disability or incapacity

SAE is collected in "Adverse Events Log" CRF page with answer "Yes" to question "Is this adverse event Serious".

Procedure related SAE

A procedure related SAE meets both procedure-related AE and SAE definitions.

Study device related SAE

A study device related SAE meets both device-related AE and SAE definitions.

AE by Maximum Severity

Based on investigator's assessment, the severity of adverse events is classed as mild, moderate, or severe. Only the highest reported severity of a given adverse event is counted for the individual subject.

AE leading to Death

AE leading to death is collected in "Adverse Events Log" CRF page with answer "Fatal" to question "Outcome".

Procedure related AE Leading to Death

A procedure related AE leading to death meets both procedure related AE and AE leading to death definitions.

Study device related AE Leading to Death

A study device related AE leading to death meets both study device related AE and AE leading to death definitions.

SIR Classification System

A major complication is defined as an event that lead to substantial morbidity and disability that increases the level of care, or results in hospital admission, or substantially lengthens the hospital stay.

AE complications are classed by outcome by SIR Classification System as following:

- A. No therapy, no consequence
- B. Nominal therapy, no consequence; includes overnight admission for observation only
- C. Require therapy, minor hospitalization (< 48 hours)
- D. Require major therapy, unplanned increase in level of care prolonged hospitalization (> 48 hours)
- E. Permanent adverse sequelae
- F. Death.

The minor complications (A, B) and the major complications (C-F) will be presented by preferred term.

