7.1.7. Safety Evaluation Method

1) Description of safety parameters

The safety parameters in this study are all AEs and SAEs for 30 days after any ablation procedure (original or additional); after 30 days post an ablation procedure through the end of the study, only SAEs will be reported and assessed. The safety endpoint is the rate of AEs and SAEs reported at each analysis and cumulatively throughout the entire study period.

2) Selection of method and time to evaluate, record, and analyze the safety parameters

Confidential Page 31 of 61

NeuWave Medical, Inc. NEU_2017_07

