06 AUGUST 2020, VERSION: 4.0

Patients will be assessed for all AEs and SAEs for 30 days after any ablation procedure (original or additional); after 30 days post an ablation procedure through the end of the study, only SAEs will be reported. The safety parameters are recorded on the e-CRF according to the investigator's record, medical record, and all other related source documents, which are collected at each follow-up visit.

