06 AUGUST 2020, VERSION: 4.0

Procedure details:

- o Complete procedure time.
- Ablation time.
- Anatomical location of ablation.
- Number of probe placement attempts.
- Number of ablations.
- o Ablation maximum power and time used for each probe and ablation.
- Guidance method used.
- Number of ultrasound and/or CT scans performed for probe and margin assessment.
- Device accountability: type(s) and number of probes used.
- Any update to relevant concomitant medications. Exclude the elements of the medications that compose the anesthesia.
- All AEs and SAEs.

Visit 2B—Post ablation

The following data must be collected post ablation (up to 7 days after an ablation procedure):

- Pain, using the NPRS.
- Quality of Life questionnaires: EORTC QLQ-C30 and liver-specific EORTC QLQ-HCC18.
- MRI scans of the liver (within 7 days after completion of ablation procedure to confirm complete tumor ablation). The MRI scans will be reviewed for reconciliation with the data provided by the treating physician regarding the ablation.
- Laboratory tests.
 - Coagulation tests (PT, APTT, and INR);
 - Liver function tests (AST, ALT, GGT, albumin, indirect, direct and total bilirubin, and total protein).
 - Renal function tests (Urea, creatinine, and electrolytes [sodium, potassium, and chloride]).
 - o Complete blood count (differential cell count and platelet count).
 - Alpha-fetoprotein (AFP) test.
- ECOG performance evaluation.

Confidential Page 38 of 61

NeuWave Medical, Inc. NEU 2017 07

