14.4. Reporting Procedure, Contact Information

The investigator should provide the sufficient treatment for any AE of any patients, including the laboratory detection value with clinical significance whether or not it is related to this study.

From ablation of the patient, all AEs related to the patient's participation in this study should be followed up until the event is resolved, or if the event causes the permanent damage, it should be followed up until the event is stable and the clinical outcome is determined.

All AEs and SAEs will be reported for 30 days after any ablation procedure (original or additional); after 30 days post an ablation procedure through the end of the study, only SAEs will be reported. All AEs should be followed up, until the AE is resolved, stable or the study is completed.

The investigator should record the nature, severity, treatment and outcome of the AE or SAE, and determine whether it is related to the study device, or the ablation procedure specified in the study protocol. The investigator will report all AEs to the Sponsor via the study database EDC.

The investigator must submit any SAEs that occurred in the study and the device deficiencies that may cause an SAE, to the Sponsor and National Medical Products Administration (NMPA) (or designated person) immediately after being informed of the event. If required by the Sponsor, the further information should be provided.

All SAEs need to be followed up until the event is resolved (with or without sequela). When the event is not resolved or stable at the end of study, the medical monitor in this clinical study will decide whether it is necessary to collect the further follow-up information.

The investigator and Sponsor should report the SAEs which occurred in the study, and the device deficiencies that may cause an SAE, to the regulatory authorities at every level according to the requirements of laws and regulations.

For all SAEs and device deficiencies that may cause SAEs, the Sponsor should report to the Food and Drug Administration where the clinical study was filed and the competent department of health and Family Planning Commission within 5 work days after awareness. The Sponsor should also inform other clinical trial institutions/sites and investigators that participate in the trial and inform the Ethics Committees by their medical device clinical trial management departments in a timely manner.

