8.1.2 Study day

The onset day of AE is calculated from the date of first microwave ablation administrated to the date of the AE start date, as follows:

Onset Day = (date of event - date of first microwave ablation + 1) if date of event happens on or later than date of ablation.

Onset Day = (date of event – date of first microwave ablation) if date of event happens earlier than date of ablation.

Study Day will be calculated from the reference start date (date of first microwave ablation) and will be used to show start/stop day of assessments and events.

Study Day = (date of event – date of first microwave ablation + 1) if date of event happens on or later than date of ablation

Study Day = (date of event – date of first microwave ablation) if date of event happens earlier than date of ablation.

In the situation where the event date is partial or missing, the Onset Day/Study Day and any corresponding durations will appear missing.

If a date is partial, no imputation will be done except for adverse events (AEs). If the day of AE start is missing, the first day of the month is considered as the start date, unless the month is the same month as the month of ablation, in which case day will be set equal to the day of ablation. If month part is missing, the AE start date is imputed as the first day of the year, unless the same year of ablation, in which case day will be set equal to the day of ablation. If the day or month of AE end is missing, the day will be imputed as the end day of the month or the year, unless the same month or year as the day of ablation. If the imputed date happens later than death date, the date is replaced with death date.

Based on the protocol, there will be no imputation of missing data for any parameters or for early terminated patients.

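### The SAP opens the adverse event window at consent and limits no AE table to onset on or after ablation, so any pre-ablation event that is entered would count in the safety rates

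*SAP*

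**What the plan says.** **SAP.** Section 8.5.1 opens the window at consent: "AEs will be recorded since date of informed consent signature until 30 days after any ablation procedure except SAEs with 36 months follow-up period". It then lists the AE tables (overview, SOC and PT, procedure-related, device-related, serious, maximum severity, SIR class), with percentages over all subjects in the FAS or SAF. On attribution it adds: "Events marked with missing relationship with study device is considered as device-related AE". Section 8.1.2 gives a separate onset-day formula for use "if date of event happens earlier than date of ablation". It also moves an AE start date with a missing day to the ablation day when the month is the month of ablation, and does the same with a missing month in the year of ablation.

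**Protocol.** Section 7.1.7 defines the endpoint data: "The safety parameters in this study are all AEs and SAEs for 30 days after any ablation procedure (original or additional". After those 30 days only SAEs are reported. The same section, on timing, says "Patients will be assessed for all AEs and SAEs for 30 days after any ablation procedure (original or additional", and section 14.4 repeats it: "All AEs and SAEs will be reported for 30 days after any ablation procedure (original or additional". Section 14.4 also ties follow-up of events to treatment: "From ablation of the patient, all AEs related to the patient's participation in this study should be followed up". In Table 1 the AE row is empty at Screening. In section 7.2.4 the Visit 1 list has no AE item, and Visit 2A, the day of ablation, is the first visit to list one: "All AEs and SAEs".

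**The concern.** The two documents start the clock at different points, and the later one, which governs the tables, starts it before the device has been used. A programmer who follows SAP 8.5.1 as written has no instruction to leave out an event that began between consent and ablation. If such an event is in the database for an ablated subject, it goes into the overview, SOC/PT, severity and SIR tables, and into the SAE tables if serious. If the device-relationship field is missing, it also goes into the device-related tables.

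The safety endpoint is the rate of AEs and SAEs, and safety is part of the key objective. The study has one arm, so no control group carries the same background events. Protocol 8.4 sets no acceptance threshold: performance is judged from all the data, in the context of other HCC therapies. The descriptive rates are therefore the evidence, and they should describe the period in which the device could have acted.

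**Working it through.** **1. Denominators.** Inputs from SAP section 7: 100 subjects with one-year data, 20% dropout, 3 run-in patients at each of 4 sites. 100 / (1 − 0.20) = 125, and 125 + 4 × 3 = 137. The plan's total is reproduced. If every enrolled subject is ablated, the FAS has 125 subjects and the SAF 137.

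**2. Does anything in the SAP restore the protocol's start?**
- There is no treatment-emergent definition in 8.5.1 or elsewhere.
- None of the listed AE tables carries an onset condition.
- The formula in 8.1.2 for events before ablation is a dating convention. It provides for such events and neither includes nor excludes them.
- SAP 8.6 describes the first interim safety summary as running from the perioperative period to one month. That is a description, not a filter.
- The SAF requires that ablation was attempted, so events in subjects who were screened but never ablated stay out.

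**3. Share of the initial all-AE window before exposure.** Ablation day to day 30 is 31 days. Screening, including consent, falls within 14 days before ablation (Table 1; protocol 7.2.4). Share = pre / (pre + 31).

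| Days from consent to ablation | Share |
|---|---|
| 14 (maximum) | 14/45 = 31% |
| 7 | 7/38 = 18% |
| 3 | 3/34 = 9% |

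A repeat ablation opens a further 30-day window, so these shares apply to the initial window only.

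**4. Share of the SAE window.** With the SAP's conversion, 36 × 30.4375 = 1,096 days. 14 / (14 + 1,096) = 1.3% at most.

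**5. Effect of one subject.** 1/125 = 0.80 points in the FAS and 1/137 = 0.73 points in the SAF, for a subject with no other AE counted in the same table row. A subject who already has an event in that row adds nothing.

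**6. Illustration, with an assumed background rate.** The documents give none. Let p be the proportion of subjects with at least one background AE in 31 days, at a constant hazard. With pre-ablation days fully collected, the proportion becomes 1 − (1 − p)^((31 + pre)/31).

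| Assumed p | 3 days | 7 days | 14 days |
|---|---|---|---|
| 5% | 5.5% | 6.1% | 7.2% |
| 10% | 10.9% | 12.1% | 14.2% |
| 20% | 21.7% | 23.9% | 27.7% |

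These are upper-range figures. They presume complete AE collection during Screening, which the protocol does not schedule.

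**7. Would a plain date filter be enough?** Not quite. An event that began before ablation, with the start day missing and the month equal to the ablation month, is re-dated by SAP 8.1.2 to the ablation day and passes the filter. A cut at the start of energy delivery would err the other way: it could drop anaesthesia or probe-placement events on the day of ablation. Visit 2A collects these, and the SAP's date-only arithmetic cannot separate them.

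**The case against.** The best reply is that the data may hardly exist. The SAP sentence is about recording, and recording follows the protocol, which has no AE item at Screening. One cannot cite the empty Screening cell as proof of a conflict and then size the harm as if Screening AEs were fully collected. This stands, and it makes the consequence conditional.

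The protocol is also less explicit than it could be. Section 14.1 asks for all AEs to be recorded, and no single sentence says that collection begins at ablation. That start is inferred from the 30-day wording, Table 1 and the visit lists. The inference is sound, because all of these agree and nothing in the protocol sets a start at consent.

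A reader might infer that pre-ablation events would routinely be charged to the device, because the relationship field would be left blank before any device use. The documents do not support this. Protocol 14.1 has the investigator assess relationship for every AE and offers a Not Related category, with lack of a temporal relationship among its criteria. Section 9 has missing data points queried. Three things must coincide: a pre-ablation event is entered, the field is blank, and the query stays unresolved. The missing-means-related rule is itself a conservative choice, in line with the protocol's treatment of unassessable events as possibly related.

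A reader might also take the month that protocol 7.1.5 allows for Screening and conclude that about half of the window precedes treatment. That figure is a rounded description of participation time. The operative limit in Table 1 and section 7.2.4 is 14 days, and it covers consent.

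Finally, no hypothesis or threshold depends on these rates, and the AE listings show start dates and relationship, so early events remain visible. That lowers the stakes but does not supply the missing restriction.

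**Conclusion.** The point holds as a conflict between the SAP and the protocol, with a conditional effect on the safety tables. Read literally, the SAP counts any pre-ablation event entered for an ablated subject in the AE and SAE rates, and as device-related if the device relationship is still missing after query.

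The pre-exposure share is at most 31% of the initial all-AE window and about 1% of the SAE window. The first figure assumes the full 14 days between consent and ablation. Both are shares of observation time, which equal shares of background events only at a constant background rate; they are not shares of the reported AE rate. If sites collect AEs on the protocol's schedule, the effect is small.

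The documents do not show that such events will be entered, nor that they will be attributed to the device. They show only that the SAP would not keep them out. The correction is cheap and worth making before the AE programs are run.

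**What to change.** 1. Reconcile the opening sentence of SAP 8.5.1 with protocol 7.1.7, 14.4 and Table 1.
2. Restrict every AE and SAE summary table to events with an onset date on or after the date of first ablation. Keep all events of that day, including those before energy delivery. State the rule in dates, because SAP 8.1.1 calls the ablation day Day 0 while the formula in 8.1.2 gives it the value 1.
3. List events between consent and ablation separately, so that no safety information is lost.
4. Apply the rule that a missing relationship counts as device-related only to events on or after the ablation date.
5. For a partial start date in the month or year of ablation, keep the SAP 8.1.2 imputation to the ablation day unless the end date or other recorded data show that the event began earlier. Run the filter on the imputed date, since 8.1.2 leaves the onset day missing for partial dates.

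The cost is SAP wording, one filter with a check for partial dates in the AE programs, and one extra listing. No new data are needed.
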